#### **8.3.6.1. Intervention-emergent ALT/AST Elevations Including Immune-related Hepatic AEs**

Elevated liver enzyme activity can be triggered by the underlying HBV disease as well as potentially by the study intervention. Management of intervention-emergent ALT/AST elevations is described below.

Hepatic AEs, including elevated liver function tests and, infrequently, drug-induced-liver-injuries (DILI) have been observed following treatment with anti-PD-1 therapies. Early recognition and treatment of elevated liver function tests and DILI are critical to their management. Participants should be advised to seek medical evaluation if they notice jaundice (yellow appearance of skin or sclera) or if they develop bruising, bleeding, or right-sided abdominal pain. Investigators should monitor liver function tests (included in chemistry laboratory test) during the study.

Any treatment-emergent elevation of ALT and/or AST  $\geq 3x$  ULN and  $\geq 3x$  nadir (ie, lowest value during study participation) should trigger an assessment of confounding factors (alcohol intake, change in concomitant medication, and comorbidities), and should trigger a confirmatory study visit to repeat laboratory testing of ALT, AST, ALP, bilirubin (total and direct), INR, albumin, HBV DNA. After nivolumab initiation, antinuclear antibodies, anti-smooth muscle antibodies, anti-neutrophil cytoplasmic antibodies, and gamma globulin should be added as part of the confirmatory laboratory testing to assess potential immune-related hepatic AEs. Additional tests should be considered based on clinical judgement: Hepatitis A, Delta, C, E: IgM anti-HAV; delta IgM, IgG and polymerase chain reaction (PCR), HCV RNA, IgM and IgG anti-HEV, HEV RNA; CMV, herpes simplex virus (HSV), Epstein-Barr virus (EBV) infection; IgM and IgG anti-CMV, IgM and IgG anti-HSV; IgM and IgG anti-EBV, PCR; HIV; Ig electrophoresis. The confirmatory visit should be scheduled as soon as possible within 7 days of the receipt of the initial ALT/AST results. Additional PBMC and AFP samples may be taken in case of ALT flares, upon discussion with the sponsor, which may require an unscheduled visit.

In case the repeat laboratory testing shows an isolated ALT/AST elevation (ie, with stable albumin, bilirubin [total and direct], and INR) the participant may continue study intervention.

JNJ-3989 (and nivolumab if already started) should be discontinued in case of:

- confirmed ALT elevation >1,000 U/L, OR

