- ALT and/or AST  $\geq 3x$  ULN and  $\geq 3x$  nadir associated with any of the following laboratory results or clinical symptoms:
  - INR  $\geq 1.5$ , OR
  - direct bilirubin >1.5x ULN, OR
  - serum albumin <3.0 g/dL, OR
  - ascites, hepatic encephalopathy, or liver-related symptoms (eg, severe fatigue, nausea, vomiting, right upper quadrant pain in the absence of an alternative medical explanation), OR
  - other indication of reduced liver function.

NA treatment should be continued. The participant should be monitored (laboratory testing of ALT, AST, ALP, bilirubin [total and direct], INR, albumin, and HBV DNA) on a weekly basis or more frequently, or as per clinical judgement until ALT and AST levels have returned to 50% of the maximal value and, if present, liver-related symptoms have improved.

In case of ALT elevation  $\geq 3x$  ULN during the first 4 weeks, administration of JNJ-3989 should be discussed with the sponsor.

Prior to starting nivolumab treatment, the participant's most recent ALT value (tested by local or central lab) should be <3x ULN with no change in autoimmune status. In case the administration of nivolumab would not be in the interest of the participant, this should be discussed with the sponsor.

In case of suspicion of immune-related hepatic events, please refer to [Table 5](#) for more frequent visit monitoring and nivolumab discontinuation criteria. JNJ-3989 might be continued after nivolumab discontinuation following discussion with the sponsor. NA treatment should be continued.

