**Table 5: Management of Immune-Related Hepatic Adverse Events**

| Grade   | Recommended Actions  |
|---|--|
| Grade 1 AST and/or ALT (<3xULN)   | Monitor liver function tests (included in chemistry laboratory test) as outlined in the Schedule of Activities ; |
| 
 
• Grade 2 AST and/or ALT (<math>\geq 3xULN</math> to <5xULN), or
 
• Grade 2 ALP (<math>\geq 2.5xULN</math> to <5xULN),
 
 
with total bilirubin <2.5 mg/dL and INR<1.5
 | Monitor within 7 days and on a weekly basis until return to 50% of the maximal value;  |

| Grade  | Recommended Actions  |
|--|--|
| 
 
• Grade 3-4 ALT and/or AST (<math>\geq 5 \times \text{ULN}</math>) or
 
• Grade 3-4 ALP (<math>\geq 5 \times \text{ULN}</math>) or
 
• total bilirubin <math>\geq 2.5 \text{ mg/dL}</math> or
 
• INR <math>\geq 1.5</math>
 
 | 
Monitor every 2-3 days;
 
In case:
 
 
• Liver tests (ALT, AST or ALP) worsen within 7 days +/- histological confirmation of immune-mediated hepatitis or
 
• Total bilirubin <math>\geq 2.5 \text{ mg/dL}</math> or
 
• INR <math>\geq 1.5</math>
 
 
Immediately
 
 
• Start steroids 0.5 mg/kg/d (or 1 mg/kg/d if severe)
 
• Discontinue nivolumab
 
 
No improvement: Increase steroids to 1 or 2 mg/kg/d depending on previous dose
 
If no improvement within 7 days at 2 mg/kg/d, add 1 steroid pulse of 500 mg
(repeat 3 times according to liver test evolution)
 
Improvement LFT return to <math>\leq</math> Grade 1: taper steroids over 6-8 weeks to 10-12 weeks depending on the dose given.
 
No improvement: consider adding mycophenolate mofetil 1 g bid; if no response within 5 days consider other immunosuppressants per local guidelines
 |

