### 8.3.6.2. Infusion-related Reactions and Other Immune-related Adverse Events

Therapy with immunomodulator agents such as nivolumab can lead to specific irAEs that differ in nature, severity and duration as compared to AEs caused by agents with a different mode of action. Early recognition and management of these irAEs may mitigate more severe/subsequent toxicity. However, differential diagnoses including non-inflammatory etiologies and/or concomitant medication should be evaluated according to standard medical practice.

Management algorithms have been developed to assist investigators in assessing and managing specific irAEs following administration of nivolumab (NSPC; NUSPI 2016). These guidelines are presented below and should be followed for nivolumab:

1. Participants should be evaluated to identify any alternative etiology.
2. In the absence of a clear alternative etiology, all events of an inflammatory nature should be considered immune-related.
3. Symptomatic and topical therapy should be considered for low-grade events.
4. Systemic corticosteroids should be considered for a persistent low-grade event or for a severe event.
5. More potent immunosuppressives should be considered for events not responding to systemic corticosteroids (eg, anti-tumor necrosis factor [TNF] agents or mycophenolate).

Refer to Section 7.1 Discontinuation of study intervention for stopping rules.

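### The nadir condition in the Section 8.3.6.1 repeat-visit trigger leaves a narrow gap: ALT ≥3x ULN with raised direct bilirubin need not be retested if ALT has never fallen to ULN

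*Protocol*

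**What the plan says.** **Repeat visit (Section 8.3.6.1).** An ALT and/or AST of at least 3x ULN and at least 3x "nadir (ie, lowest value during study participation) should trigger an assessment of confounding factors" and a repeat visit. On timing: "The confirmatory visit should be scheduled as soon as possible within 7 days of the receipt of the initial ALT/AST results". The repeat panel is how the protocol identifies the reassuring pattern: "In case the repeat laboratory testing shows an isolated ALT/AST elevation (ie, with stable albumin, bilirubin [total and direct], and INR"), study intervention may go on.

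**Stops for JNJ-3989.** Section 8.3.6.1 stops JNJ-3989 (and nivolumab, once started) in two situations:

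- a confirmed ALT above 1,000 U/L;
- ALT and/or AST at least 3x ULN and at least 3x "nadir associated with any of the following laboratory results or clinical symptoms", namely INR of 1.5 or more, direct bilirubin above 1.5x ULN, albumin below 3.0 g/dL, or symptoms or other signs of reduced liver function.

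Section 7.1.1 adds a stop with no ALT condition. There, direct bilirubin above 1.5x ULN counts only in combination with INR of at least 1.5x ULN or albumin below 3.0 g/dL. Clinical decompensation also counts.

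**Entry.** Inclusion criterion A03 (Section 5.1) admits ALT below 2.0x ULN.

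**Table 5.** This table has no nadir term. For ALT or AST from 3x to below 5x ULN with total bilirubin below 2.5 mg/dL and INR below 1.5, it says "Monitor within 7 days and on a weekly basis until return to 50% of the maximal value"; worse values are monitored every 2 to 3 days. Its entry condition is suspicion: "In case of suspicion of immune-related hepatic events, please refer to" Table 5. Its drug action is on nivolumab: "JNJ-3989 might be continued after nivolumab discontinuation following discussion with the sponsor". After nivolumab, Section 8.3.6.2 makes an immune cause the default: "In the absence of a clear alternative etiology, all events of an inflammatory nature should be considered immune-related".

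**The concern.** The two conditions are joined by AND, so the effective threshold is the higher of 3x ULN and 3x nadir. A participant who starts and stays above ULN therefore needs a larger rise before anything is required. That is reasonable for an isolated ALT fluctuation. It is harder to defend when direct bilirubin is already above 1.5x ULN, because such a result is not isolated on the protocol's own description, yet the test meant to sort isolated from non-isolated rises is not required.

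The stake is patient safety. Section 2.3.2.2 names ALT elevation as an important potential risk of JNJ-3989 itself, so the weeks before nivolumab matter. Direct bilirubin above 1.2x ULN is an exclusion at entry (A02, Section 5.2), so a value above 1.5x ULN on study would generally be new.

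**Working it through.** No sample size, power or alpha figure is involved; the check is of rule logic. All enzyme values are multiples of ULN.

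**Step 1. When is the gap possible?** With nadir n, the trigger is T = max(3, 3n). The gap is 3 ≤ ALT < 3n, which requires n > 1. One ALT at or below ULN during participation closes it.

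**Step 2. How wide is it?** If the screening ALT counts toward the nadir, A03 gives n < 2, so the gap lies below 3 × 2 = 6x ULN.

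| Nadir | Trigger (3 × nadir, minimum 3) | ALT range with no required repeat visit |
|---|---|---|
| ≤1.0 | 3.0 | none |
| 1.1 | 3.3 | 3.0 to <3.3 |
| 1.2 | 3.6 | 3.0 to <3.6 |
| 1.5 | 4.5 | 3.0 to <4.5 |
| 1.8 | 5.4 | 3.0 to <5.4 |
| 1.99 | 5.97 | 3.0 to <5.97 |

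At ALT 4.0 the gap opens once the nadir exceeds 4.0 / 3 = 1.33.

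**Step 3. Apply every written rule to one case.** ALT 4.0, AST below 3, direct bilirubin 2.0x ULN, INR 1.0, albumin 4.0 g/dL, no symptoms.

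| Rule | Nadir 1.3 (3 × nadir = 3.9) | Nadir 1.5 (3 × nadir = 4.5) |
|---|---|---|
| 8.3.6.1 repeat visit | yes | no |
| 8.3.6.1 organ-function stop | yes (bilirubin) | no |
| 8.3.6.1 ALT >1,000 U/L stop | no | no |
| 7.1.1 bilirubin stop | no (INR, albumin normal) | no (INR, albumin normal) |

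The documents give no ALT ULN. For an assumed ULN of 30 to 60 U/L, 6x ULN is 180 to 360 U/L. The 1,000 U/L stop could reach the gap only if ULN exceeded 1,000 / 6 ≈ 167 U/L.

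**Step 4. Which doses are exposed?** JNJ-3989 is given at Weeks 0, 1, 2, 3, 4, 8, 12, 16, 20 and 24. Section 6.4 requires sponsor discussion of ALT ≥3x ULN in the first 4 weeks. Nivolumab starts at Week 16, after that day's JNJ-3989 injection (Section 1.3.1, footnote l). The doses in between are Weeks 8, 12 and 16, or 3 of 10.

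The SAP's Amendment 1 rationale records that nivolumab dosing was halted on 20 June 2023 while JNJ-3989 continued. Week 16 is Day 113, and 20 June 2023 minus 112 days is 28 February 2023. A participant with Day 1 after about that date would not have reached nivolumab, and the exposed doses become Weeks 8 to 24, or 5 of 10. The number of such participants is not given.

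**Step 5. What does the missing visit cost in time?** Scheduled chemistry at Weeks 8, 12 and 16 falls on Days 57, 85 and 113, so 28 days apart. A triggered visit comes within 7 days of receiving results: 28 − 7 = 21 days sooner, less laboratory turnaround.

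**The case against.** The strongest reply is that a number is missing, not a safeguard. Much of it stands:

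- Section 8.3.6 has ALT/AST elevations, as events of special interest, reported to the Medical Monitor, with no nadir term and no week limit. A reader might infer from Section 6.4 that ALT ≥3x ULN reaches the sponsor only in the first 4 weeks; Section 8.3.6 does not support that.
- ALT should be below 3x ULN before nivolumab starts (Sections 6.1 and 8.3.6.1; footnote o). A reader might infer that nivolumab could be started in the worked case; this gate blocks it. It does not block JNJ-3989.
- Recent laboratory results must be reviewed before every dose (footnote m). Section 7.1.1 requires a stop when the investigator judges it necessary for safety. Unscheduled visits are allowed for ALT elevations (Section 1.3.1, footnote a).
- After nivolumab, Table 5 normally supplies monitoring within 7 days. A reader might point to the 56-day visit spacing after FU Week 24 as the general consequence. It is not: no study drug remains by then, and Table 5 applies by default unless another cause is clear or nivolumab was never given.
- Many conditions must coincide. In REEF-1 (Section 2.2.3.1) there were 13 flares in 425 participants, 11 of them in currently untreated participants, so 2 in a population like this one. None had a concurrent bilirubin rise. That count uses the same nadir definition, however, so it cannot show how often gap cases occurred.

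It can also be said that the nadir term is the programme's deliberate flare definition, and that a fix limited to the visit leaves the stop asymmetric. Both are true. The visit still supplies the repeat results on which the investigator's stopping decision would rest.

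What does not stand is the suggestion that this cover amounts to a repeat test. Before nivolumab, none of these provisions sets a threshold at which one is required.

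**Conclusion.** The gap is real on the text and small. It needs a nadir above 1x and below 2x ULN (if the screening ALT counts), ALT at least 3x ULN but below 3x nadir, AST not qualifying, direct bilirubin above 1.5x ULN, INR below 1.5, albumin at least 3.0 g/dL and no symptoms. In that state this protocol contains no threshold-based repeat visit or JNJ-3989 stop. In practice it concerns mainly the Week 8, 12 and 16 doses of JNJ-3989, plus participants who never received nivolumab because of the halt or who have a clear non-immune cause.

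Assumptions and limits: the INR ULN is taken as at least 1.0, so that INR below 1.5 also misses the 7.1.1 limit. Frequency is unknown and probably very low. The Master Protocol's safety sections were not available, so the conclusion covers only the rules written here. Section 7.1 does name 7.1.1 and 7.1.2 as the stopping criteria.

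A reader might blame the different INR limits (1.5 in Section 8.3.6.1, 1.5x ULN in Section 7.1.1). They are not the cause: the worked case has INR 1.0.

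This is a cheap improvement in patient safety, not a finding that participants are left without oversight.

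**What to change.** In Section 8.3.6.1, add to the repeat-visit trigger:

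*OR ALT and/or AST ≥3x ULN, whatever the nadir, with direct bilirubin >1.5x ULN, INR ≥1.5 (not on anticoagulation therapy) or albumin <3.0 g/dL.*

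The INR and albumin terms are included because the protocol judges whether a rise is isolated on all three markers. The anticoagulation qualifier follows the INR row of Appendix 8. Leave the flare definition and all stopping rules, including Section 7.1.1, unchanged. Because the clause is joined by OR, no visit now required is lost. In the worked case it brings a repeat panel within 7 days of the result.

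Cost: one clause of protocol wording, using an existing visit type and existing tests. Downside: a few extra confirmatory visits, since ALT or AST of at least 3x ULN must coincide with an abnormal liver-function marker.

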**Table 5: Management of Immune-Related Hepatic Adverse Events**

| Grade   | Recommended Actions  |
|---|--|
| Grade 1 AST and/or ALT (<3xULN)   | Monitor liver function tests (included in chemistry laboratory test) as outlined in the Schedule of Activities ; |
| 
 
• Grade 2 AST and/or ALT (<math>\geq 3xULN</math> to <5xULN), or
 
• Grade 2 ALP (<math>\geq 2.5xULN</math> to <5xULN),
 
 
with total bilirubin <2.5 mg/dL and INR<1.5
 | Monitor within 7 days and on a weekly basis until return to 50% of the maximal value;  |

| Grade  | Recommended Actions  |
|--|--|
| 
 
• Grade 3-4 ALT and/or AST (<math>\geq 5 \times \text{ULN}</math>) or
 
• Grade 3-4 ALP (<math>\geq 5 \times \text{ULN}</math>) or
 
• total bilirubin <math>\geq 2.5 \text{ mg/dL}</math> or
 
• INR <math>\geq 1.5</math>
 
 | 
Monitor every 2-3 days;
 
In case:
 
 
• Liver tests (ALT, AST or ALP) worsen within 7 days +/- histological confirmation of immune-mediated hepatitis or
 
• Total bilirubin <math>\geq 2.5 \text{ mg/dL}</math> or
 
• INR <math>\geq 1.5</math>
 
 
Immediately
 
 
• Start steroids 0.5 mg/kg/d (or 1 mg/kg/d if severe)
 
• Discontinue nivolumab
 
 
No improvement: Increase steroids to 1 or 2 mg/kg/d depending on previous dose
 
If no improvement within 7 days at 2 mg/kg/d, add 1 steroid pulse of 500 mg
(repeat 3 times according to liver test evolution)
 
Improvement LFT return to <math>\leq</math> Grade 1: taper steroids over 6-8 weeks to 10-12 weeks depending on the dose given.
 
No improvement: consider adding mycophenolate mofetil 1 g bid; if no response within 5 days consider other immunosuppressants per local guidelines
 |

### 8.3.6.2. Infusion-related Reactions and Other Immune-related Adverse Events

Therapy with immunomodulator agents such as nivolumab can lead to specific irAEs that differ in nature, severity and duration as compared to AEs caused by agents with a different mode of action. Early recognition and management of these irAEs may mitigate more severe/subsequent toxicity. However, differential diagnoses including non-inflammatory etiologies and/or concomitant medication should be evaluated according to standard medical practice.

Management algorithms have been developed to assist investigators in assessing and managing specific irAEs following administration of nivolumab (NSPC; NUSPI 2016). These guidelines are presented below and should be followed for nivolumab:

1. Participants should be evaluated to identify any alternative etiology.
2. In the absence of a clear alternative etiology, all events of an inflammatory nature should be considered immune-related.
3. Symptomatic and topical therapy should be considered for low-grade events.
4. Systemic corticosteroids should be considered for a persistent low-grade event or for a severe event.
5. More potent immunosuppressives should be considered for events not responding to systemic corticosteroids (eg, anti-tumor necrosis factor [TNF] agents or mycophenolate).

Refer to Section 7.1 Discontinuation of study intervention for stopping rules.

#### 8.3.6.2.1. Gastrointestinal Adverse Events

Diarrhea and colitis have been observed in participants receiving anti-PD-1 therapies. Early recognition and treatment of diarrhea and colitis are critical to their management. Participants should be advised to seek immediate medical evaluation if they develop new-onset diarrhea, blood in stool, or severe abdominal pain or if they have worsening of baseline diarrhea. In case of

treatment-emergent colitis  $\geq$ Grade 2, medical assessment should include testing for cytomegalovirus (CMV). In participants with pre-existing diverticulosis and/or diverticulitis receiving concomitant medication with corticosteroids, nonsteroidal anti-inflammatory drugs (NSAIDs), and opioid analgesics together with anti-PD-1 therapies, diverticular perforation has been observed. Refer to Table 6 for the management of immune-related gastrointestinal AEs.

**Table 6: Management of Immune-Related Gastrointestinal Adverse Events**

| Grade     | Recommended Actions   |
|-----------|---|
| Grade 1   | Symptomatic treatment according to institutional standards
Close monitoring; instruct participant to report worsening immediately and treat as Grade $\geq 2$  |
| Grade 2   | $\leq 5$ days: Symptomatic treatment according to institutional standards
$> 5$ days or recurrence: 0.5–1.0 mg/kg/d methylprednisolone; consider prophylactic antibiotics; discontinue nivolumab
Persistence or worsening despite steroids <math>> 3</math> days: treat as Grade 3/4
Improvement to <math>\leq</math>Grade 1: taper steroids over at least 4 weeks, consider prophylactic antibiotics for opportunistic infections, resume study therapy per protocol   |
| Grade 3-4 | Immediately: 1.0–2.0 mg/kg/d methylprednisolone IV; consider prophylactic antibiotics and lower endoscopy (ie, proctoscopy, sigmoidoscopy or full colonoscopy depending on the participant's symptoms; discontinue nivolumab
Note that known or suspected bowel perforation is a contraindication to endoscopy.
Persistence <math>> 3</math> days or recurrence: add infliximab 5 mg/kg (if no contraindication such as perforation or sepsis)
Improvement to <math>\leq</math>Grade 2 within <math>\leq 3</math> days: taper steroids over at least 4 weeks |
| General   | The oral corticosteroid equivalent of the recommended IV dose may be considered for ambulatory patients; the lower bioavailability of oral corticosteroids needs to be considered.
Clinical caution should be exercised, for participants receiving concomitant medications of corticosteroids, NSAID, or opioid analgesics. In addition, monitor for signs and symptoms of potential perforation, especially in participants with known diverticular disease. Narcotics should be used with caution as pain medicines may mask the signs of colonic perforation                           |

### 8.3.6.2.2. Neurological Adverse Events

Neurological AEs have been uncommonly observed following treatment with anti-PD-1 therapies. Neurological AEs can manifest as central abnormalities (eg, aseptic meningitis or encephalitis) or peripheral sensory/motor neuropathies (eg, Guillain-Barre Syndrome). The onset has been observed as early as after a single treatment. Early recognition and treatment of neurologic AEs is critical to their management (refer to Table 7). Participants should be advised to seek medical evaluation if they notice impairment in motor function (eg, weakness), changes in sensation (eg, numbness), or symptoms suggestive of possible central nervous system abnormalities such as new headache or mental status changes.

**Table 7: Management of Neurological Adverse Events**

| Grade     | Recommended Actions   |
|-----------|---|
| Grade 1   | Monitor per protocol
Worsening: treat as $\geq$ Grade 2   |
| Grade 2   | Immediately: treat symptoms according to institutional standards; consider 0.5-1.0 mg/kg/d methylprednisolone IV or oral equivalent; discontinue nivolumab
Worsening: treat as Grade 3-4   |
| Grade 3-4 | Immediately: consult neurologist; treat symptoms according to institutional standards; start 1.0-2.0 mg/kg/d methylprednisolone IV or IV equivalent; prophylactic antibiotics; discontinue nivolumab |

| Grade          | Recommended Actions   |
|----------------|---|
|                | Worsening or atypical presentation: consider immunoglobulins IV (IVIG) or other immunosuppressive therapies according to institutional standards
Improvement to <math>\leq</math>Grade 2: taper steroids over at least 4 weeks                       |
| General | Participants on IV steroids may be switched to an equivalent dose of oral corticosteroids (eg, prednisone) at start of tapering or earlier, once sustained clinical improvement is observed. The lower bioavailability of oral corticosteroids needs to be considered |

